### 3.2 Primary Endpoints

The primary endpoint is the number of reported adverse events and serious adverse events, including their severity, seriousness, and treatment relatedness.

### 3.3 Secondary Endpoints

1. Change in mouse specific IgE.
2. Change in mouse specific IgG and IgG4.
3. Change in in-vitro mouse antigen binding to B-cells

## 4 Selection of Participants and Clinical Sites/Laboratories

### 4.1 Rationale for Study Population

Because the combination of mouse allergy and mouse exposure is one of the most important factors contributing to the asthma morbidity seen in inner city children with asthma, a major ICAC goal is to conduct an immunotherapy efficacy trial that will include mouse allergen. Given that there has been so little study of mouse immunotherapy, adults will be studied in this safety trial.

### 4.2 Participant Inclusion Criteria

Participants who meet all of the following criteria are eligible for enrollment. Participants may be reassessed if not initially eligible. Participants are eligible if they:

1. Are male or female adults, 18 through 55 years of age at recruitment.
2. Have a history of asthma for a minimum of 1 year before study entry.
  - i. A diagnosis of asthma will be defined as a report by the participant that they have had a clinical diagnosis of asthma made by a clinician over a year ago.
  - ii. The participant must have persistent asthma defined by the current need for at least 100 mcg of fluticasone per day or the equivalent of another inhaled corticosteroid.
  - iii. The participant's asthma must be well controlled as defined by:
    1. A FEV1 greater than or equal to 70% predicted with or without controller medication. (see Section 8.2).
    2. An Asthma Control Test (ACT) score  $\geq 20$ .
3. Are sensitive to mouse as documented by a positive ( $\geq 3$  mm greater than negative control) skin prick test result (using the same extract used for immunotherapy) and detectable mouse specific IgE ( $\geq 0.10$  kUA/L).
4. Have no known contraindications to therapy with glycerinated mouse allergenic extract.
5. Are willing to sign the written Informed Consent prior to initiation of any study procedure.

### 4.3 Participant Exclusion Criteria

Participants who meet any of the following criteria are not eligible for enrollment but may be reassessed. Participants are ineligible if they:

1. Are pregnant or lactating. Females must be abstinent or use a medically acceptable birth control method throughout the study (e.g. oral, subcutaneous, mechanical, or surgical contraception).
2. Cannot perform spirometry at Screening.
3. Have an asthma severity classification at Screening of severe persistent, using the NAEPP classification, as evidenced by at least one of the following:
  - a. Require a dose of greater than 500 mcg of fluticasone per day or the equivalent of another inhaled corticosteroid.
  - b. Have received more than 2 courses of oral or parenteral corticosteroids within the last 12 months.
  - c. Have been treated with depot steroids within the last 3 months.
  - d. Have been hospitalized for asthma within the 6 months prior to Screening.

- e. Have had a life-threatening asthma exacerbation that required intubation, mechanical ventilation, or that resulted in a hypoxic seizure within 2 years prior to Screening.
4. Do not have access to a phone (needed for scheduling appointments).
5. Have received allergen immunotherapy (SLIT or SCIT) in the last 12 months prior to Screening or who plan to initiate or resume allergen immunotherapy during the study.
6. Have previously been treated with anti-IgE therapy within 1 year of Screening.
7. Have received an investigational drug in the 30 days prior to Screening or who plan to use an investigational drug during the study.
8. Refuse to sign the Epinephrine Auto-injector Training Form.

Participants who meet any of the following criteria are not eligible for enrollment and may not be reassessed.

Participants are ineligible if they:

1. Do not primarily speak English.
2. Plan to move from the area during the study period.
3. Have a history of idiopathic anaphylaxis within the past 5 years or anaphylaxis grade 2 or higher as defined in section 12.3.2, Grading Criteria for Anaphylaxis.
4. Have unstable angina, significant arrhythmia, uncontrolled hypertension, history of autoimmune disease, or other chronic or immunological diseases that in the opinion of the investigator might interfere with the evaluation of the investigational agent or pose additional risk to the participant.
5. Are using tricyclic antidepressants or beta-adrenergic blocker drugs (both oral and topical).
6. Have not received and refuse to receive the Flu Vaccine.

## 5 Known and Potential Risks and Benefits to Participants

### 5.1 Risks of Study Procedures

Risks of exposing participants to allergens via immunotherapy include, but are not limited to: itching of the mouth, ears, and throat, itching or swelling of the eyes, nasal congestion, sneezing, rhinorrhea, oral or throat angioedema, cough, chest tightness, wheezing, gastrointestinal symptoms (vomiting, diarrhea, abdominal pain), skin symptoms (rash, hives, swelling, itching), and anaphylaxis. We expect that the main sign/symptom experienced by participants will be localized swelling at the injection site occurring within 30 minutes after administration of the immunotherapy injection. Large local reactions associated with allergen immunotherapy are common, with a frequency ranging from 26% to 86% of injections.

In published studies of SCIT, systemic anaphylactic reactions with other inhalant allergens have been reported to occur in from 1% of patients to as many as 36% of patients receiving SCIT using a rush schedule. This study does not involve a rush immunotherapy schedule. Fatalities are very rare but have been reported, as have specific risk factors for fatal reactions, which include unstable asthma, beta-blocker therapy, rush immunotherapy, and use of high doses of potent standardized extracts. In our SCITCO study, in 10 adults undergoing six months of SCIT, there were 2 serious adverse events reported, neither of which were considered related to the therapy.

The risks to a fetus are unknown and SCIT is generally not initiated during pregnancy. Pregnant females will be excluded from the present protocol. Urine pregnancy testing will be performed at the Screening Visit and monthly

thereafter to ensure no pregnant female will be entered into the study and any female becoming pregnant during the course of the study will be discontinued.

## **5.2 Potential Benefits**

There are no known potential benefits for the participant in this trial. The participant's allergic rhinitis or asthma may or may not improve while in this study. In the longer term, this study may promote the further development of mouse SCIT for asthma and allergic rhinitis, which could be a major advance in the care of individuals with these conditions who are allergic to mouse antigens.

# **6 Investigational Agent**

## **6.1 Investigational Agent**

Participants will receive escalating doses of glycerinated mouse allergenic extract or placebo administered via the subcutaneous route up to a Maximum Study Dose (MSD) of 0.4 ml of extract at a concentration of 1:20 wt/vol.

### **6.1.1 Formulation, Packaging, and Labeling**

The investigational agent is glycerinated mouse allergenic extract (50% Glycerin). The active ingredient of the investigational agent is a non-standardized allergen derived from the extraction and purification of proteins from mouse epithelia (*mouse epithelial extract*).

The investigational agent will be manufactured Greer laboratories, Lenoir NC. Glycerinated Mouse Epithelia (*Mus musculus*) allergic extract is approved in the United States for diagnostic skin testing and immunotherapy by subcutaneous injection (US License NO. 308). It has been used in humans for at least 35 years. Dosage, Preparation, and Administration

Initial dilutions of the mouse allergenic extract needed for dose escalation will be prepared by a research pharmacy. Complete details can be found in the Manual of Operations (MOP), which is based on the DAIT Pharmacy manual and AAAAI practice parameters.

Participants will receive escalating doses of glycerinated mouse allergenic extract administered via the subcutaneous route up to a MSD of 0.4 ml of extract at a concentration of 1:20 wt/vol. See Section 8.45 for the dose escalation schedule.

The investigational agent will be shipped by the manufacturer as per their approved method. On site the investigational agent will be stored at -2° C.

## **6.2 Drug Accountability**

Under Title 21 of the Code of Federal Regulations (21CFR §312.62) the investigator will maintain adequate records of the disposition of the investigational agent, including the date and quantity of the drug received, to whom the drug was dispensed (participant-by-participant accounting), and a detailed accounting of any drug accidentally or deliberately destroyed.

Records for receipt, storage, use, and disposition will be maintained by the study site. A drug-dispensing log will be kept current for each participant. This log will contain the identification of each participant and the date and quantity of drug dispensed.

All records regarding the disposition of the investigational product will be available for inspection.

Unused product will be destroyed by the study site after accountability requirements have been met and approval has been received from DAIT/NIAID.

### **6.3 Assessment of Participant Compliance with Investigational Agent**

As participants will receive their injections in the clinic, compliance will be monitored by assessing the number of completed and missed clinic visits.

### **6.4 Toxicity Prevention and Management**

In the case of a reaction to the study medication, dosing will be altered in the following manner:

- For local reactions 6-11 cm in diameter, the dose will be repeated.
- For local reactions greater than 12 cm, the dose will be reduced to the prior dose during escalation and cut by 50% while on maintenance with re-escalation the following week.
- For mild systemic symptoms (Grade 1 anaphylaxis), the dose will be reduced by 2 doses during escalation or reduced cut by 75% while on maintenance with re-escalation over the next 2 weeks.

### **6.5 Premature Discontinuation of Investigational Agent**

Participants who are unable to complete the first 8 injections following the Dose Initiation Visit will be unable to proceed to the maintenance period and may be replaced (see Section 11.2, Participant Stopping Rules and Withdrawal Criteria). Subjects unable to continue beyond that point will not be replaced. A final blood sample will be drawn on participants who need to discontinue therapy.

Study therapy may be prematurely discontinued for any participant for any of the following reasons:

1. SAE related to investigational agent
2. Anaphylactic reaction grade 2 or 3 (see Section 12.3.2, Grading Criteria for Anaphylaxis)
3. Inability to tolerate the build up to or the MSD due to excessive discomfort/symptoms or large local reactions after a second attempt at dose escalation
4. Development of any serious medical illness whose natural history, sequela, or treatment would be worsened or impaired by continuation in the protocol
5. The study treatment is no longer in the best interest of the participant
6. Pregnancy

## **7 Other Medications**

### **7.1 Concomitant Medications**

#### **7.1.1 Protocol-mandated**

Not applicable.

#### **7.1.2 Other permitted concomitant medications**

During the study, after the initial skin testing, rhinitis and asthma medications will be permitted along with other maintenance medications, aside from those excluded in Section 4.3, Participant Exclusion Criteria. A dose of greater than 500 mcg of fluticasone per day or the equivalent of another inhaled corticosteroid may be used short-term to control an asthma exacerbation.

## **7.2 Prophylactic Medications**

Not applicable.

## **7.3 Prohibited Medications**

1. A regular dose of greater than 500 mcg of fluticasone per day or the equivalent of another inhaled corticosteroid.
2. Allergen immunotherapy (SLIT or SCIT)
3. Anti-IgE therapy
4. Tricyclic antidepressants
5. Beta-adrenergic blocker drugs (both oral and topical)
6. Any investigational drug

Antihistamines will need to be suspended prior to skin testing at the screening and final visits.

## **7.4 Rescue Medications**

Participants may use antihistamines as needed for large local reactions to the injections. In the event of a rare, but severe reaction to the glycerinated mouse allergenic extract away from the study site, participants will receive 2 epinephrine auto-injectors during the Dose Initiation Visit. Participants must sign the epinephrine auto-injector training form and understand its use before they can be enrolled in the study and receive the investigational agent.

# **8 Study Procedures**

## **8.1 Recruitment**

The study center may use any IRB-approved means to identify potential participants. Examples include hospital, clinic, or emergency department admission records; investigators' specialty clinic records; and advertising (in public locations and on the radio). Potential participants will be screened and recruited using a standardized questionnaire that collects contact information and inclusion/exclusion criteria information. Participants may be recruited by phone or in person.

Retention methods involve a number of different approaches. Appointment reminder cards are given at each visit. We will use an appointment reminder system that consists of phone calls and/or text messages several days and one day prior to scheduled appointments for confirmation. To facilitate telephone contact with subjects whose phone service may change during the study, at least three telephone contact numbers (relatives, neighbors, friends) will be collected for each subject. This has proven to be an effective strategy in previous ICAC studies. Those who have no obvious characteristics making them ineligible and who are interested will be invited to the clinic for a Screening Visit.

## **8.2 Screening/Baseline Visit**

This research study will be explained in lay terms to each potential research participant. The potential participant will provide informed consent before he or she undergoes any screening study procedures. Written informed consent and Health Insurance Portability and Accountability Act (HIPAA) authorization will be obtained from all participants at the beginning of this visit. Study procedures will be stopped and the participant will be deemed ineligible for the study at any point during the Screening Visit if and when they fail to meet eligibility criteria.

After the consent is signed, participants will undergo screening study procedures, including prick skin tests with mouse allergenic extract to ensure participants are sensitive to the test product, since those who do not react to mouse are excluded from the remainder of the study. In addition, participants will be tested with: American cockroach, German

cockroach, cat, dog, Alternaria, house dust mite, and selected seasonal aeroallergen allergenic extracts, as specified in the study MOP, to characterize the study population.

A medical history will be taken and a targeted physical examination will be performed to verify the participant's suitability for inclusion in the study. A urine pregnancy test will also be performed on all female participants.

Spirometry will be performed by all participants to verify the participant's suitability for inclusion in the study. Candidates whose FEV1 is less than 70% of predicted normal will be excluded; however, if their asthma can be brought under control within 2 months, as described in Section 8.3, they are eligible for rescreening.

Blood will be collected by venipuncture for mouse-specific IgE antibody testing.

Participants must agree to receive a flu vaccine if they are in the study during flu season. Participants will be offered a flu vaccine when it becomes available. Participants may choose to receive the flu vaccine outside of the study.

Participants who have both a positive skin prick test to mouse allergenic extract and a mouse-specific IgE  $\geq 0.10$  kU/L and are considered eligible for the study, and at the discretion of the study clinician, will be invited to proceed to the Dose Initiation Visit.

### **8.3      Asthma Control Optional Visits**

Participants whose FEV1 is less than 70% of predicted normal or whose asthma is not well controlled as defined by the inclusion and exclusion criteria may qualify for rescreening if their condition improves while recruitment is ongoing.

### **8.4      Dose Initiation**

The Dose Initiation Visit will be scheduled according to the guidelines in the MOP.

Written instructions on the proper use, storage, and administration of the epinephrine auto-injector will be given to participants at the Dose Initiation Visit. Participants must sign the epinephrine auto-injector training form and understand its use before being enrolled in the study and receiving the investigational agent. Participants will receive 2 epinephrine auto-injectors during the Dose Initiation Visit.

Blood will be collected by venipuncture and will be tested for assessment of biomarkers of allergen immunotherapy, such as mouse-specific IgE and IgG4 antibodies.

The first injection will contain 0.05 mL of 1:10,000 concentration of 1:20 w/v glycerinated mouse allergenic extract as detailed in the Dose Escalation Table 8.5.1. Each injection will be administered by the research staff along with any rescue medications, as required. Refer to the MOP for information on handling treatment-related reactions. Prior to the administration of each dose of allergenic extract, the study clinician will assess the eligibility of the participant to receive the allergenic extract injection and will review any side-effects or adverse reactions experienced by the participant. Participants will report symptoms, using a questionnaire, 30 minutes after each injection is administered in order to identify side effects. During all dosing visits, a clinician and appropriate emergency supplies will be readily available to treat any adverse reactions. Study participants will remain at the clinic for observation for at least 30 minutes after each allergenic extract injection.

All participants receiving the initial dose will have information gathered and assessed on any delayed reactions or side effects experienced, regardless of whether or not they continue on to the 24 week treatment course.

## 8.5 Follow-up

### 8.5.1 Dose Escalation

Dose escalation will be conducted by the following schedule:

**Table 8.5.1 Dose Escalation**

Dose #	Week* #	Concentration	Volume	Approximate Dose	Mus m 1
1	1	1:10,000	0.05 ml		
2	1	1:10,000	0.10 ml		
3	2	1:10,000	0.20 ml		
4	2	1:10,000	0.40 ml		
5	3	1:1,000	0.05 ml		
6	3	1:1,000	0.10 ml		
7	4	1:1,000	0.20 ml		
8	4	1:1,000	0.40 ml		
9	5	1:100	0.05 ml		
10	5	1:100	0.10 ml		
11	6	1:100	0.20 ml		
12	6	1:100	0.40 ml		
13	7	1:10	0.05 ml		
14	7	1:10	0.10 ml		
15	8	1:10	0.20 ml		
16	8	1:10	0.40 ml		
17	9	1:1	0.05 ml		
18	9	1:1	0.10 ml		
19	10	1:1	0.15 ml		
20	10	1:1	0.20 ml		
21	11**	1:1	0.30 ml		
22	11	1:1	0.40 ml		
Maint.***	12-24	1:1	0.40 ml		6.2 mcg

\* During dose escalation, 2 injections will be given each week separated by at least 2 days

\*\* Dose escalation may be accomplished over a maximum of 18 weeks

\*\*\* During maintenance, doses will be given every 2 weeks

For the first 11 weeks of the 24-week treatment course participants will receive two injections per week, separated by at least 2 days, at the escalating doses as described in Table 8.5.1. Dose escalation can be delayed at any point if there are excessive large local reactions or other concerns, although to continue on to maintenance each subject will need to reach the maximum study dose in a maximum of 18 weeks. A clinician and appropriate emergency supplies will be readily available to treat any adverse reactions. Participants will be discharged after the 30 minute waiting period if they show no signs or symptoms greater than mild, as defined in Section 12.3.1, or at the discretion of the study clinician.

Dose escalation will continue according to the schedule unless there are lapses in dosing or reactions occur. Dosing will be modified as follows for lapses in dosing or reactions:

- For a lapse in dosing of more than two weeks during escalation, the dose from the previous visit will be repeated.
- For a lapse in dosing of more than three weeks during escalation, the subject will be discontinued from the protocol.
- For one missed dosing visit while on maintenance, the maintenance dose will be continued.
- For two missed maintenance doses while on maintenance, the dose will be reduced by 50% and re-escalated the following week.
- For more than two consecutive missed dosing visits while on maintenance, the subject will be discontinued from the protocol.
- For local reactions 6-11 cm in diameter, the dose will be repeated.
- For local reactions greater than 12 cm, the dose will be reduced to the prior dose during escalation and cut by 50% while on maintenance with re-escalation the following week.
- For mild systemic symptoms (Grade 1 anaphylaxis), the dose will be reduced by 2 doses during escalation or reduced cut by 75% while on maintenance with re-escalation over the next 2 weeks.

Participants who are unable to reach the Maximum Study Dose by 18 weeks following the Dose Initiation Visit will be unable to proceed to the maintenance period and may be replaced (see Section 11.2, Participant Stopping Rules and Withdrawal Criteria).

### **8.5.2 Maintenance Visits**

For the remaining time of the 24 week treatment course, participants will receive one injection of investigational agent every 2 weeks.

Participants will be instructed to immediately report any severe sign or symptom possibly related to the subcutaneous administration of the investigational agent and to contact the study site when they need medical advice. For those participants with asthma, exacerbations will be handled through an approach consistent with standard clinical practice as described in the MOP.

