### **11.2 Participant Stopping Rules and Withdrawal Criteria**

Participants will be withdrawn from the study if the following events occur:

1. SAE related to investigational agent
2. Anaphylactic reaction grade 2 or 3 (see Section 12.3.2, Grading Criteria for Anaphylaxis)
3. Inability to tolerate the build up to or the MSD due to excessive discomfort/symptoms or large local reactions after a second attempt at dose escalation
4. The need to start immunotherapy or any chronic immunosuppressive medications (e.g., greater than 2 courses of oral or parenteral corticosteroids)
5. Require a dose of greater than 500 mcg of fluticasone per day or the equivalent of another inhaled corticosteroid to maintain asthma control
6. Development of any serious medical illness whose natural history, sequela, or treatment would be worsened or impaired by continuation in the protocol
7. The study treatment is no longer in the best interest of the participant
8. Participant is “lost to follow-up,” as defined in the MOP
9. Pregnancy
10. A lapse in dosing of more than 3 weeks during escalation
11. Missing more than 2 consecutive treatment visits during maintenance
12. Missing 25% or more of all maintenance visits (miss more than 2 maintenance visits)

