### **12.3 Grading and Attribution of Adverse Events**

#### **12.3.1 Grading Criteria**

The study site will grade the severity of adverse events experienced by the study subjects according to the criteria set forth in the National Cancer Institute's Common Terminology Criteria for Adverse Events (CTCAE) (Version 4.03, June 14, 2010). This document (referred to herein as the NCI-CTCAE manual) provides a common language to describe levels of severity, to analyze and interpret data, and to articulate the clinical significance of all adverse events. The NCI-CTCAE has been reviewed by the Protocol Chair and has been deemed appropriate for the subject population to be studied in this protocol.

Adverse events will be graded on a scale from 1 to 5 according to the following standards in the NCI-CTCAE manual:

Grade 1 = mild adverse event.

Grade 2 = moderate adverse event.

Grade 3 = severe and undesirable adverse event.

Grade 4 = life-threatening or disabling adverse event.

Grade 5 = death.

For grading an abnormal value or result of a clinical or laboratory evaluation (including, but not limited to, a radiograph, an ultrasound, an electrocardiogram etc.), a treatment-emergent adverse event is defined as an increase in grade from baseline or from the last post-baseline value that doesn't meet grading criteria. Changes in grade from screening to baseline will also be recorded as adverse events, but are not treatment-emergent. If a specific event or result from a given clinical or laboratory evaluation is not included in the NCI-CTCAE manual, then an abnormal result would be considered an adverse event if changes in therapy or monitoring are implemented as a result of the event/result.

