**Table 12.3.2 Grading System of Severity of Anaphylaxis**

Grade	Defined By
1. Mild (skin & subcutaneous tissues, GI, &/or mild respiratory)	Flushing, urticaria, periorbital or facial angioedema; mild dyspnea, wheeze or upper respiratory symptoms; mild abdominal pain and/or emesis
2. Moderate (mild symptoms + features suggesting moderate respiratory, cardiovascular or GI symptoms)	Marked dysphagia, hoarseness, and/or stridor; SOB, wheezing & retractions; crampy abdominal pain, recurrent vomiting and/or diarrhea; and/or mild dizziness
3. Severe (hypoxia, hypotension, or neurological compromise)	Cyanosis or SpO 2 < 92% at any stage, hypotension, confusion, collapse, loss of consciousness; or incontinence

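### The immediate-report instruction in section 8.5.2 is worded for severe reactions, one grade above the moderate (grade 2) anaphylaxis that triggers withdrawal and counts toward suspension

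*Combined protocol and SAP*

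**What the plan says.** Section 8.5.2 (Maintenance Visits) gives participants two instructions in one sentence. The first is "Participants will be instructed to immediately report any severe sign or symptom possibly related to the subcutaneous administration of the investigational agent"; the second is "and to contact the study site when they need medical advice". Neither refers to a grading scale, and the second has no time limit.

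Both severity scales in the protocol put moderate at grade 2 and severe at grade 3. For adverse events in general, section 12.3.1 has "Grade 2 = moderate adverse event". For anaphylaxis, Table 12.3.2 has "2. Moderate (mild symptoms + features suggesting moderate respiratory, cardiovascular or GI symptoms", with stridor, wheezing with retractions and marked dysphagia among its features.

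Section 11.2 lists the events for which participants will be withdrawn, among them "Anaphylactic reaction grade 2 or 3 (see Section 12.3.2, Grading Criteria for Anaphylaxis". Under section 11.5, related grade 2 anaphylaxis in at least 2 participants suspends enrollment and treatment.

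Elsewhere the protocol sets its threshold at moderate. Under section 8.5.1, participants leave after the 30-minute wait "if they show no signs or symptoms greater than mild, as defined in Section 12.3.1", or at the clinician's discretion. Section 8.6 requires follow-up of moderate or severe symptoms at the last visit, and section 8.9 allows an unscheduled visit for moderate to severe symptoms.

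**The concern.** The event that matters for withdrawal and suspension is a grade 2 reaction, but the only immediate report asked of participants is worded one grade higher. Observation in the clinic lasts at least 30 minutes, so a later reaction happens where only the participant sees it. If that participant does not think of it as severe and does not feel a need for advice, nothing in the protocol asks for a call. The site would then normally learn of it through the adverse event assessment at the next visit.

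Two things could be late: the withdrawal of the person who reacted, and the count toward the two-participant suspension rule. If the unreported reaction is one of the two that meet the rule, other participants may still be receiving injections after the boundary has been crossed.

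The instruction also stands only under Maintenance Visits, although auto-injectors for reactions away from the site are handed out at the Dose Initiation Visit (7.4).

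**Working it through.** **1. Thresholds side by side**

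| Place | Purpose | Threshold |
|---|---|---|
| 8.5.1 | Discharge after an injection | Nothing above mild, tied to 12.3.1, or clinician's discretion |
| 8.6 | Follow-up after the last visit | Moderate or severe |
| 8.9 | Unscheduled visit (optional) | Moderate to severe |
| 8.5.2 | Immediate report from home | Severe, no scale cited |
| 11.2 | Withdrawal (mandatory) | Anaphylaxis grade 2 (moderate) or 3 |
| 11.5 | Suspension | Related grade 2 in at least 2 participants |

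Section 6.5 says therapy *may* be discontinued for the same anaphylaxis grades, but 11.2 is mandatory, so a grade 2 reaction does require withdrawal.

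**2. Reproducing the plan's injection count**

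Table 8.5.1 has 22 escalation doses, the last in week 11. Maintenance runs over weeks 12 to 24, every 2 weeks.

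- First maintenance dose in week 13: weeks 13, 15, 17, 19, 21 and 23 give 6 doses, and 22 + 6 = 28.
- First maintenance dose in week 12: 7 doses, and 22 + 7 = 29.

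Both agree with the approximately 28 injections in section 13.6. The week-13 start matches exactly and is used below.

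**3. Time to the next visit**

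- Maintenance, nominal: 2 × 7 = 14 days.
- Maintenance under the calendar-week window of section 8.10: a visit on day *d* of its week (Monday = 0) is followed by one 14 − *d* to 20 − *d* days later. Over all weekdays that is 8 to 20 days. For a Monday–Friday clinic (an assumption), the shortest gap is Friday to Monday, 14 − 4 = 10 days, and the longest is Monday to Friday, 14 + 4 = 18 days.
- One missed maintenance visit: 2 × 14 = 28 days nominally. The plan continues treatment in that case: "For one missed dosing visit while on maintenance, the maintenance dose will be continued".
- Escalation: "During dose escalation, 2 injections will be given each week separated by at least 2 days". On a fixed weekly pattern with one gap of *g* days, *g* ≥ 2, the other is 7 − *g*, so gaps run from 2 to 5 days.

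**4. How many injections are followed by the long gap**

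The 6 maintenance doses, plus dose 22 (week 11, next injection in week 13): (6 + 1)/28 = 25%. The interval from the last dose to the Final Visit is not given; leaving that gap out gives 6/28 = 21%. With a week-12 start, dose 22 has only about a one-week gap and the share is 7/29 = 24%. All of these injections are scheduled at the full 0.4 ml of 1:1 extract.

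**5. How often the suspension rule could come into play at all**

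The documents give no grade 2 rate for this extract. With an assumed risk *p* per participant, independent between participants,

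P(at least 2 of *n*) = 1 − (1 − *p*)^*n* − *n p* (1 − *p*)^(*n* − 1).

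| *p* (assumed) | *n* = 10 | *n* = 12 |
|---|---|---|
| 1% | 0.4% | 0.6% |
| 5% | 8.6% | 11.8% |
| 10% | 26.4% | 34.1% |

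For each *p* this is a ceiling. The case at issue also needs a qualifying reaction to occur away from the site, after one of the long-gap injections, and to go unreported. The documents give no basis for those further fractions.

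**The case against.** The strongest reply is that *severe* in 8.5.2 is a lay word. It cites no scale and applies to a sign or symptom, whereas Table 12.3.2 grades a whole reaction. Many people would call stridor, or wheezing with retractions, severe and phone at once. Section 7.4 uses the same word for the reaction away from the site for which auto-injectors are issued. The second limb of 8.5.2 is also an instruction, not merely a permission, and it has no grade threshold. This stands: many grade 2 reactions would probably be phoned in. The gap covers only those that are neither seen as severe nor felt to need advice.

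Other routes also narrow it. Section 8.1 plans calls or texts several days and one day before appointments. They are for confirmation and carry no stated adverse event question, but a reaction could come out then. Section 8.4 commits to gathering information on delayed reactions, without a time limit, and refers to the MOP for handling treatment-related reactions. The MOP and the auto-injector training form are not among the documents and may already ask for a prompt call.

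The pre-dose review in 8.4 should catch the event before the person who reacted is dosed again. A reader might infer that this person would be re-dosed unrecognised; the documents do not support that.

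A reader might also multiply the 14-day delay by the dosing of others (about 1 injection each in maintenance, up to 4 each in escalation) and present the total as harm that better wording would avert. That does not follow either. Accrual timing is not given, so the number of others on treatment is unknown and could be none. Suspension needs two related events, with final attribution by DAIT/NIAID (12.3.3). A non-serious event has as its stated route to the Medical Monitor a monthly report (12.8.1), which can take longer than 14 days. The 24-hour rule in 12.5.1 covers serious events only and starts at discovery.

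**Conclusion.** The mismatch is real and minor. The protocol attaches withdrawal and a suspension count to a moderate reaction but words its only immediate-report instruction to participants for a severe one, and no other section requires prompt report of a moderate reaction away from the site.

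The size that can be stated is the possible delay: nominally 14 days (10 to 18 for a Monday–Friday clinic) after about a quarter of injections, about 28 days if a visit is missed, and less if a reminder contact brings the event out. During escalation it is normally 2 to 5 days. The consequence is a late withdrawal and a late suspension count. I judge the probability low because several conditions must coincide; it cannot be calculated from the documents.

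The conclusion assumes that the MOP and training form do not already close the gap and that the first maintenance dose falls about two weeks after dose 22. It does not extend to a claim that the plan leaves grade 2 reactions undetected, or that a given number of injections would be avoided.

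**What to change.** In section 8.5.2, replace *any severe sign or symptom* with *any moderate or severe sign or symptom, or any use of the epinephrine auto-injector*. Give the same instruction in section 8.4 from the first injection. It then also covers dose 22, which is formally an escalation dose but is followed by the long gap. If the MOP or the training form already says this, bring 8.5.2 into line with it.

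The cost is a wording change and some extra calls, including calls about moderate asthma symptoms; their number cannot be estimated from the documents. No scheduled visit or procedure is added, and any resulting unscheduled visit is already allowed by 8.9. The change speeds only the step from participant to site. The onward route for non-serious events stays as it is.
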